8.2 DETERMINATION OF SAMPLE SIZE

Using an alpha=0.05, 80% power and event rate estimates of 6.8% in the untreated and 3.7% in the treated population, the estimated sample size would be 860 patients per arm or 1720 patients in total for the full trial. Estimating a 10% lost to follow up this would lead to a required sample of 1892 patients. Enrollment data, event rates, and study drop out will be assessed in this pilot trial will aid in the calculation of the required sample size for the full trial. Due to the low event rates, small differences in the event rates in either patient population will lead to large changes in the sample size required.

For the purposes of the pilot the target sample size is 100 patients with plans to run the pilot trial for 1 year. This would involve 4-6 enrollments/month at the coordinating centre in Ottawa, and 2 enrollments per month at the sites of Halifax and Edmonton.

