2. STUDY SYNOPSIS

Title: A pilot study assessing the feasibility of a randomized controlled trial investigating primary thromboprophylaxis with rivaroxaban in patients with malignancy and central venous catheters (CVC)

Short Title: The TRIM-Line

Protocol Version: 28Feb2018 Version 1.1

Principal Investigators: [name] and [name]

Sponsor: OHRI

Study Centres:

The Ottawa Hospital, General Campus, Ottawa, ON
QEII Health Sciences Centre, Halifax, Nova Scotia
University of Alberta Hospital, Edmonton, Alberta

Timeline: February 2019-September2019

Purpose of Pilot Trial

To determine the feasibility of conducting a multicentre randomized open label-controlled trial evaluating the use of prophylactic dose rivaroxaban to prevent CVC associated venous thromboembolism(VTE) among cancer patients.

Purpose of Full Trial

The purpose of the full trial is to determine the efficacy and safety of prophylactic dose rivaroxaban to prevent CVC associated VTE among cancer patients.

Pilot Trial Endpoints

The primary feasibility outcome for the pilot study is the number of participants recruited per centre per month. We will obtain baseline details of the patient's type, location and treatment of cancer, comorbidities and medications. Secondary feasibility outcomes of the pilot study will include, consent rates, loss to follow up, adherence to therapy defining 80% or greater medication taken as having good adherence to study drug, proportion of screened patients who meet eligibility criteria.

We will document reasons for non-consent in order to assist recruitment for the larger multicentre trial.

Full Trial Endpoints

For the full multicentre trial the outcomes would be as follows: primary outcome symptomatic, radiographically confirmed VTE. Secondary outcomes include major and clinically relevant non-major bleeding (CRNMB), CVC life span, premature CVC removal, CVC lumen occlusion, CVC associated infection and death.

Design

This is a pilot study to be conducted at 3 Canadian Centres. The Ottawa Hospital, QEII Health Science Centre and University of Alberta Hospital. It is an open label randomized controlled trial.

Consenting participants, meeting eligibility criteria will be randomized at the time of enrollment to one of two groups.

Rivaroxaban 10mg po daily x 90 days

OR

Observation

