Participants in the treatment arm will have study drug dispensed at Day 1 and take medication for 90 days. Follow up visits (in person or phone) will occur at Day 30 (+/- 3 days) and Day 90 (+/- 3 days) month and 3 months post enrollment. Overall, participants will be followed for 3 months. Adverse events will be collected for the first 90 days.

Number of participants

100

Inclusion and Exclusion Criteria

Inclusion criteria:

Patients 18 years of age or older with a new or existing diagnosis of cancer with a CVC inserted in the last 72 hours.

Exclusion criteria:

- 1) CVC in place for >72 hours
- 2) Patient requires anticoagulation for other indication
- 3) Concomitant use of dual antiplatelet therapy
- 4) Prior VTE
- 5) Major bleeding event in the last 6 weeks
- 6) Patient on concomitant medication with known interaction with rivaroxaban (eg. CYP3A4 inhibitor)
- 7) Pregnancy (documentation of use of effective contraception if sexually active or negative B- Hcg required)
- 8) Known renal failure, based on Creatinine clearance <30 mL/min (Cockcroft-Gault) (in the previous 3 months)*
- 9) Documented severe liver disease (eg. acute clinical hepatitis, chronic active hepatitis, cirrhosis or ALT >3ULN) (in the previous 3 months)*
- 10) Known thrombocytopenia < 50x 10⁹/L (in the previous 3 months)*
- 11) Allergy to rivaroxaban
- 12) Life expectancy <6 months
- 13) History of condition at increased bleeding risk including, but not limited to:
 - a) Major surgical procedure or trauma within 30 days before the randomization visit
 - b) Clinically significant gastrointestinal bleeding within 6 months before the randomization visit
 - c) History of intracranial, intraocular, spinal, or atraumatic intra-articular bleeding
 - d) Chronic hemorrhagic disorder
 - e) Known intracranial neoplasm, arteriovenous malformation, or aneurysm
 - f) Sustained uncontrolled hypertension: systolic blood pressure ≥180 mmHg or diastolic blood pressure ≥100 mmHg
- 14) Primary malignancy diagnosis of basal cell or squamous cell carcinoma of the skin or acute leukemia or myelodysplastic syndrome
- 15) Geographic inaccessibility
- 16) Refused or unable to obtain consent

* Baseline platelet count for inclusion/exclusion to be drawn within 2 weeks of enrolment.

SCHEDULE OF MANDATORY EVENTS

	Screening, Baseline and Randomization	Day 30 +/- 3 days	Day 90 +/- 3 days
Consent	✓		
Inclusion/Exclusion	✓		
Demographic	✓		
Randomization	✓		
Labs	✓		
History	✓		
Cancer Treatments	✓		

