4.3 TRIAL INTERVENTION

Eligible and consenting patients will receive rivaroxaban 10 mg tablets to be taken once daily, starting within 72 hours of CVC placement. Randomization will occur in a 1:1 ratio via a central web-based randomization system.

The study drug will be continued until the CVC is removed, until one of the study outcomes is achieved, or until the end of the follow-up (90 Days +/- 3 days). Study medication will be held if the platelet count is $50 \times 10^9/L$ or less, the CrCl falls below 30mL/min, the patient experiences bleeding or the patient is required for treatment of cancer to start on a medication or chemotherapy which has a major interaction with rivaroxaban. All patients will be followed for 90 days (+/-3 days), unless they die or withdraw permission for follow up. At the end of the trial, VTE prophylaxis will be left to the discretion of the local investigator.

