4.5 WHAT ARE THE MEASURED OUTCOMES FOR THE PILOT STUDY?

The primary feasibility outcome for the pilot study is the number of participants recruited per centre per month. We will obtain baseline details of the patient's type, location and treatment of cancer, and medications. Secondary feasibility outcomes of the pilot study will include, consent rates, loss to follow up, adherence to therapy defining 80% or greater medication taken as having good adherence to study drug, proportion of screened patients who meet eligibility criteria. We will document reasons for non-consent in order to assist recruitment for the larger multicentre trial.

For the full multicentre trial the outcomes would be as follows: primary outcome of symptomatic, radiographically confirmed VTE. Secondary outcomes include major and CRNMB, CVC life span, premature CVC removal, CVC lumen occlusion, CVC associated infection and death.

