8.1.3 PILOT TRIAL SECONDARY ANALYSES

Proportions with 95% confidence intervals will be calculated using Wilson's score method for the following secondary analyses: 1) proportion of screened subjects who meet eligibility criteria, 2) proportion of eligible subjects who provide consent, 3) proportion of withdrawals/losses to follow-up among randomized subjects, 4) proportion of sites requiring >18 months to obtain all required approvals/contracts from time of delivery of all study documents, and 5) proportion of crossover between study arms. Reasons for non-consent will be collected and analyzed using qualitative thematic analysis.

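### Minor: the synopsis allows the pilot at most 8 months and section 8.2 allows 1 year, while 100 patients at the planned rates need 10 to 12.5 months of enrolment

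*Protocol*

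**What the plan says.** The synopsis states "Timeline: February 2019-September2019" and sets the number of participants at 100. Section 8.2 gives the same number with a different duration: "the target sample size is 100 patients with plans to run the pilot trial for 1 year". It supports this with planned rates of "4-6 enrollments/month at the coordinating centre in Ottawa, and 2 enrollments per month at the sites of Halifax and Edmonton".

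Follow-up is 90 days for everyone. The synopsis says "Overall, participants will be followed for 3 months", and section 4.3 says "All patients will be followed for 90 days (+/-3 days), unless they die or withdraw permission for follow up". Neither the synopsis timeline nor the year in 8.2 says whether it includes this follow-up.

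The primary outcome in section 4.5 is "the number of participants recruited per centre per month". Among the proportions to be estimated, section 8.1.3 lists "proportion of withdrawals/losses to follow-up among randomized subjects", and 8.2 adds that "study drop out will be assessed in this pilot trial will aid in the calculation of the required sample size" for the full trial.

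For the full trial, 8.2 takes 860 patients per arm (1,720 in total) and allows for 10% loss to follow-up by planning 1,892.

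**The concern.** Two current statements in one protocol give the pilot different lengths, and the shorter one cannot deliver the stated size at the protocol's own rates. A pilot that closed in September 2019 with about 70 patients would be on plan by its monthly rates and its synopsis dates, yet well short of its target of 100. In a trial whose purpose is to test whether recruitment is feasible, the reader needs to know which plan was being tested.

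The statistical stake is precision. Fewer months and fewer patients widen the intervals for the recruitment rate and for the secondary proportions, including the dropout estimate meant to inform the size of the full trial.

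A second, separate slip sits in the same section: the dropout allowance multiplies by 1.10 where it should divide by 0.90, so the planned total does not leave the 1,720 patients that the calculation calls for.

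**Working it through.** **Inputs.** Target of 100 (synopsis and 8.2). Duration of 12 months (8.2), or February to September 2019, which is 8 months counted inclusively (synopsis). Ottawa 4 to 6 per month; Halifax and Edmonton 2 per month, read as 2 at each site (8.2). Follow-up of 90 days, taken as 3 months (synopsis, 4.3).

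**Total rate.** 4 + 2 + 2 = 8 per month to 6 + 2 + 2 = 10 per month.

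**The plan's own figure.** 12 × 8 = 96 to 12 × 10 = 120. This range contains 100, so 8.2 is consistent if its year is all enrolment.

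**Months needed for 100.** 100/10 = 10 to 100/8 = 12.5 months of enrolment. Adding 3 months to the last participant's final visit gives 13 to 15.5 months.

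**Expected number by period:**

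| Period | Months of enrolment | Expected N |
|---|---|---|
| Synopsis window, all enrolment | 8 | 64–80 |
| Synopsis window, follow-up inside it | 5 | 40–50 |
| 1 year, follow-up inside it | 9 | 72–90 |
| 1 year, all enrolment | 12 | 96–120 |

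On the reading most generous to the synopsis, the shortfall is 100 − 80 = 20 to 100 − 64 = 36 patients. If monthly counts are Poisson (an assumption), the chance of 100 or more in 8 months is 0.002% at a mean of 64 and 1.7% at a mean of 80.

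**Alternative reading of the rates.** If the 2 per month covers Halifax and Edmonton together, the total is 6 to 8 per month. Then 100 patients need 12.5 to 16.7 months, 8 months yields 48–64, and 12 months yields 72–96.

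**Effect on precision.**
- Recruitment rate, for scale only: Ottawa at an assumed 5 per month, exact Poisson 95% interval. Over 12 months (60 patients) it is 3.82 to 6.44; over 8 months (40 patients) it is 3.57 to 6.81.
- Loss to follow-up near the protocol's 10%, Wilson 95% interval: 10/100 gives 5.5% to 17.4%; 8/80 gives 5.2% to 18.5%; 6/64 gives 4.4% to 19.0%.

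**Dropout allowance.** 1,720 × 1.10 = 1,892, which reproduces the plan. After 10% loss, 1,892 × 0.90 = 1,702.8, about 1,703, or 17 below 1,720. The total that leaves 1,720 is 1,720/0.90 = 1,911.1, rounded up to 1,912. Exact power of Fisher's test for 6.8% versus 3.7% is 0.802 at 860 per arm and 0.797 at 851 per arm.

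**The case against.** The strongest reply is that the synopsis timeline is one administrative line in a version dated a year before the stated start. No test, interim look or stopping rule depends on September 2019, and nothing makes that month a hard end to recruitment. The synopsis and 8.2 agree on 100 patients, and 100 is not derived from a precision target, so a somewhat smaller number breaks no stated requirement. All of this stands, and it is why the point is minor. It does not remove the contradiction: both lines are current text and cannot both describe the same pilot at the planned rates.

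Three stronger readings are tempting and not supported.
- A reader might infer that the primary outcome is compromised. It is a rate per centre per month, so a shorter window does not bias it.
- A reader might infer that the pilot will end with only 40 to 50 patients. That requires the synopsis period to include follow-up, which the protocol does not say, and it takes the window as running from the start of February to the end of September, although no days are given.
- A reader might infer that only a full 12 months can give 100. At 10 per month, 10 months is enough.

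It is also fair to object that 1,892 belongs to a future trial whose size the pilot is meant to help recalculate. That limits its importance, but the figure is still wrong on its own inputs.

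**Conclusion.** The concern holds as a minor error. The two durations conflict, and the shorter one falls 20 to 36 patients short of the stated size even when every site recruits to plan and no time is kept for follow-up. Section 8.2 is sound on its own terms, provided that its year is enrolment time and the 2 per month applies to each of the two smaller sites. The second condition is the natural reading but an assumption; if it fails, the gap is larger and 12 months no longer reaches 100 either.

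The loss of precision is modest at 64 to 80 patients. The undercount of 20 in the full-trial total is certain arithmetic but small in effect.

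**What to change.** Make the synopsis timeline and 8.2 agree, and state in both whether the period includes the 90-day follow-up. State also that the 2 per month applies to each of Halifax and Edmonton, if that is meant. Then choose one of two routes.

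1. **Keep 100.** State that enrolment continues until 100 are enrolled, expected to take 10 to 12.5 months, followed by 90 days of follow-up. The cost is calendar time: 13 to 15.5 months in total is 1 to 3.5 months beyond 1 year and 5 to 7.5 months beyond an 8-month window, with the staff and monitoring that implies. No patients are added. Ending at a number is safer than a fixed 12 months, which at 8 per month has about a 35% chance of reaching 100 (Poisson) and at 10 per month would be expected to enrol 120.
2. **Keep a shorter period.** Restate the expected number: 64–80 for 8 months of enrolment, or 72–90 for 1 year including follow-up. This costs wording and some precision.

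In 8.2, also replace 1,892 with 1,912. This adds 20 patients to the planned full trial and nothing to the pilot.

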9 ETHICS

9.1 ETHICAL CONDUCT OF THE TRIAL

The trial will be performed in accordance with the recommendations guiding physicians in biomedical research involving human subjects adopted by the 18th World Medical Assembly (Helsinki, Finland, 1964 and later revisions), the Tri-Council Policy Statement and the ICH GCP Guidelines.

9.2 RESEARCH ETHICS BOARD (REB)

This study will be and approved with annual renewal by the Ottawa Health Science Network Research Ethics Board. REB approval will be obtained from all other participating centres prior to initiating the study at these sites.

9.3 SUBJECT INFORMATION AND CONSENT

The investigator, or his designee, will inform each subject (or the subject's acceptable representative) prior to inclusion in the trial, full and adequate verbal and written information regarding the objective and procedures of the trial and the possible risks involved. The subjects must be informed about their right to withdraw from the trial at any time. Written subject information will be given to each subject before enrolment.

Furthermore, it is the responsibility of the investigator or his designee to obtain signed informed consent (or witnessed verbal consent according to applicable regulations) from all subjects prior to inclusion in the trial.

10 DATA HANDLING AND RECORD KEEPING

10.1 PERSONAL HEALTH INFORMATION

Personal health information including Case Report Forms, evaluation forms, reports, etc. will be kept strictly confidential. All records will be stored on-site in a secure, locked facility.

Records will be destroyed after 25 years, in accordance with Health Canada Regulations.

10.2 CASE REPORT FORMS

A Case Report Form (CRF) is required and will be completed for each randomized subject. The completed original CRFs are the sole property of The Ottawa Hospital and are not to be made available in any form to third parties, except for authorized representatives of appropriate Regulatory Authorities.

10.3 RECORD RETENTION

To enable evaluations and/or audits, the investigator will keep records, including the identity of all participating subjects (sufficient information to link records, e.g., CRFs and hospital records), all original signed Informed Consent Forms, copies of all CRFs and detailed records of drug disposition. To comply with international regulations, the records are to be retained for 25 years.

11 STUDY DISSEMINATION PLAN

The results of our trial will be used by the investigators to evaluate the feasibility of a larger trial evaluating the role of the prophylactic dose rivaroxaban to reduce upper extremity DVT in cancer patients with central venous catheters. The results will provide justification to external funding agencies before a commitment is made to fund a full trial. Regardless of the results of the trial, we will strive to publish and present our data and conclusions about feasibility such that future researchers might benefit from this work.

The International Committee of Medical Journal Editors (ICMJE) member journals have adopted a trials-registration policy as a condition for publication. This policy requires that all clinical trials be registered in a public trials registry such as [ClinicalTrials.gov](https://www.clinicaltrials.gov), which is sponsored by the National Library of Medicine. It is the responsibility of the QI to register this trial in an acceptable registry on or before patient enrollment.
